Subject's rating of their 'overall satisfaction' with tirbanibulin treatment, in comparison to other topical treatment(s) will be assessed using a 5-point Likert scale of: 1: much worse; 2: somewhat worse; 3: same; 4: somewhat better; 5: much better. This 'overall satisfaction' assessment will be conducted among two Subject subgroups:

- Among Subjects who have experienced other topical treatments before start of tirbanibulin at baseline: At Week 8, compare rating of tirbanibulin treatment vs. previous topical treatment(s).
- Among Subjects who have been retreated with other topical treatments (other than tirbanibulin) between Week-8 and Week-24 visits: At Week 24, compare rating of original tirbanibulin treatment (at beginning of the study) vs. most recent topical treatment(s).

To complement the overall satisfaction question, factors associated with Subject's satisfaction rating will be assessed.

5.2.1 *Site Investigator Treatment Satisfaction Assessments*

An ad hoc satisfaction questionnaire very similar to TSQM-9 will be used to assess Site Investigators' satisfaction with tirbanibulin treatment at Weeks 8 & 24, in relation to the tirbanibulin treatment they administered to Subjects at the beginning of the study. The individual item and subscale scorings will be done similar to the original TSQM-9 questionnaire.

The same ad hoc questionnaire will also be administered at Week 24 among Site Investigators managing Subjects who are retreated with tirbanibulin in the past 16 weeks (since Week 8 visit), to solicit their satisfaction with the most recent course of tirbanibulin treatment.

Site Investigator's rating (at Weeks 8 & 24) of their satisfaction with the ability of tirbanibulin treatment to 'improve how their patient's skin looks' and 'improve their patient's skin texture' respectively, in the original treated area will be assessed. The responses will be solicited on the following 7-point Likert scale: 1: very dissatisfied; 2: moderately dissatisfied; 3: slightly dissatisfied; 4: neutral; 5: slightly satisfied; 6: moderately satisfied; 7: very satisfied. These two EPQ items will also be administered at Week 24 again among Subjects who are retreated with tirbanibulin between Week-8 and Week-24 visits, to solicit their satisfaction with the respective attributes associated with the most recent course of tirbanibulin treatment.

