(1 / 2) Much / somewhat better with tirbanibulin	n (%)
(3) Same with tirbanibulin	n (%)
(4 / 5) Somewhat / much worse with tirbanibulin	n (%)

TT4: Compared to your previous experience with topical treatment X for AK, how would you rate the convenience / ease of use (such as frequency of use, easy to follow instructions, comfortable at apply, etc.) associated with tirbanibulin (Klisyri®) treatment?

Mean (SD),
Median,Min,Max

1. Ease of use & convenience was much better with tirbanibulin	n (%)
2. Ease of use & convenience was somewhat better with tirbanibulin	n (%)
3. Ease of use & convenience was the same with tirbanibulin	n (%)
4. Ease of use & convenience was somewhat worse with tirbanibulin	n (%)
5. Ease of use & convenience was much worse with tirbanibulin	n (%)
(1 / 2) Ease of use & convenience was much / somewhat better with tirbanibulin	n (%)
(3) Ease of use & convenience was the same with tirbanibulin	n (%)
(4 / 5) Ease of use & convenience was somewhat / much worse with tirbanibulin	n (%)

TT5: Compared to your previous experience with topical treatment X for AK, how would you rate your overall satisfaction (considering the factors such as convenience/ ease of use, duration and severity of skin reactions, impact on daily life, etc.) with tirbanibulin (Klisyri®) treatment?

Mean (SD),
Median,Min,Max

1. My satisfaction is much better with tirbanibulin	n (%)
2. My satisfaction is somewhat better with tirbanibulin	n (%)
3. My satisfaction is same with tirbanibulin	n (%)
4. My satisfaction is somewhat worse with tirbanibulin	n (%)

5. My satisfaction is much worse with tirbanibulin	n (%)
(1 / 2) My satisfaction is much / somewhat better with tirbanibulin	n (%)
(3) My satisfaction is same with tirbanibulin	n (%)
(4 / 5) My satisfaction is somewhat / much worse with tirbanibulin	n (%)

Table 1.18 Subgroup Analysis of Patient Relative Satisfaction of Tirbanibulin, Regarding Duration of Skin Reactions

% Much / Somewhat Better	Week 8 n (%)	Week 24 n (%)
Subgroups		
Gender		
Male		
Female		
p -value		
Age Group		
≤ 49 years		
50 – 64 Years		
≥ 65 years		
p -value		
AK Treatment Location		
Face		
Scalp		
Both		
p -value		
Fitzpatrick Skin Type		
I / II		
III / IV / V / VI		
p -value		
Skin Photodamage		
Absent/mild		
Moderate/Severe		
p -value		
History of Skin Cancer		
Yes		
No		
p -value		
Prior Treatment Experience: Use of Cryosurgery		
Yes		
No		
p -value		

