p -value		
History of Skin Cancer		
Yes		
No		
p -value		
Prior Treatment Experience: Use of Cryosurgery		
Yes		
No		
p -value		
Prior Treatment Experience: Use of Other Topical Treatments		
Yes		
No		

p -value		
Prior Treatment Experience: Treatment Naïve at Baseline		
Yes		
No		
p -value		

P-values correspond to difference between strata within respective time periods.

Table 1.22 Subgroup Analysis of Patient's Overall Satisfaction with Tirbanibulin Relative to Previous Topical Treatments

% Much / Somewhat Better	Week 8 n (%)	Week 24 n (%)
Subgroups		
Gender		
Male		
Female		
p -value		
Age Group		
≤ 49 years		
50 – 64 Years		
≥ 65 years		
p -value		
AK Treatment Location		
Face		
Scalp		
Both		
p -value		
Fitzpatrick Skin Type		
I / II		
III / IV / V / VI		
p -value		
Skin Photodamage		
Absent/mild		
Moderate/Severe		
p -value		
History of Skin Cancer		
Yes		
No		
p -value		
Prior Treatment Experience: Use of Cryosurgery		
Yes		
No		
p -value		
Prior Treatment Experience: Use of Other Topical Treatments		
Yes		
No		

p -value		
Prior Treatment Experience: Treatment Naïve at Baseline		
Yes		
No		

P-values correspond to difference between strata within respective time periods.

Table 1.23 Factors Influencing Overall Patient Satisfaction with Tirbanibulin in the Original Treated Area

TT6_2 What factors influenced your response to the previous question (TT5) about your overall satisfaction with tirbanibulin (Klisyri®)? **Selected**

Domain	Week 8 N=x	Week 24 N=x
[TT6_2r1] Product convenience: Length of treatment, frequency, and easiness to take, etc.	n (%)	n (%)
[TT6_2r2] Product effectiveness: Impact on skin appearance.	n (%)	n (%)
[TT6_2r3] Product effectiveness: Impact on AK lesion clearance.	n (%)	n (%)
[TT6_2r4] Product effectiveness: Amount of time it takes to start working.	n (%)	n (%)
[TT6_2r5] Product side-effects: Amount of time it takes for local skin reactions to resolve.	n (%)	n (%)
[TT6_2r6] Product side-effects: Number and type of local skin reactions.	n (%)	n (%)
[TT6_2r7] Product side-effects: Severity of the local skin reactions.	n (%)	n (%)
[TT6_2r8] Product tolerability: Ability to adhere to treatment dose, or intensity.	n (%)	n (%)
[TT6_2r9] Other: TT6_2r9oe	n (%)	n (%)

Note: Data from patient DCF.

Table 1.24 Top-3 Factors Influencing Overall Patient Satisfaction with Tirbanibulin in the Original Treated Area Ranking at Week 8

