TT6_2A Among the list of factors that influenced your overall satisfaction with tirbanibulin (Klisyri®), please identify the three most important factors and rank them on a scale of importance from 1 to 3, where 1 is the first most important factor, 2 is the second most important factor and 3 is the third most important factor to you, by entering a number in the boxes next to only those factors in the following list.

Domain	Rank 1	Rank 2	Rank 3	Average Rank
[TT6A_2r1] Product convenience: Length of treatment, frequency, and easiness to take, etc. (N=x)	n (%)	n (%)	n (%)	
[TT6A_2r2] Product effectiveness: Impact on skin appearance. (N=x)	n (%)	n (%)	n (%)	
[TT6A_2r3] Product effectiveness: Impact on AK lesion clearance. (N=x)	n (%)	n (%)	n (%)	
[TT6A_2r4] Product effectiveness: Amount of time it takes to start working. (N=x)	n (%)	n (%)	n (%)	
[TT6A_2r5] Product side-effects: Amount of time it takes for local skin reactions to resolve. (N=x)	n (%)	n (%)	n (%)	
[TT6A_2r6] Product side-effects: Number and type of local skin reactions. (N=x)	n (%)	n (%)	n (%)	
[TT6A_2r7] Product side-effects: Severity of the local skin reactions. (N=x)	n (%)	n (%)	n (%)	
[TT6A_2r8] Product tolerability: Ability to adhere to treatment dose, or intensity. (N=x)	n (%)	n (%)	n (%)	
[TT6A_2r9] Other: (N=x) TT6A_2r9oe	n (%)	n (%)	n (%)	

Note: Data from patient DCF. Percentages are based on number of patients choosing a particular attribute to previous question (TT6_2).

Table 1.25 Top-3 Factors Influencing Overall Patient Satisfaction with Tirbanibulin in the Original Treated Area Ranking at Week 24

TT6_2A Among the list of factors that influenced your overall satisfaction with tirbanibulin (Klisyri®), please identify the three most important factors and rank them on a scale of importance from 1 to 3, where 1 is the first most important factor, 2 is the second most important factor and 3 is the third most important factor to you, by entering a number in the boxes next to only those factors in the following list.

Domain	Rank 1	Rank 2	Rank 3	Average Rank
[TT6A_2r1] Product convenience: Length of treatment, frequency, and easiness to take, etc. (N=x)	n (%)	n (%)	n (%)	
[TT6A_2r2] Product effectiveness: Impact on skin appearance. (N=x)	n (%)	n (%)	n (%)	
[TT6A_2r3] Product effectiveness: Impact on AK lesion clearance. (N=x)	n (%)	n (%)	n (%)	
[TT6A_2r4] Product effectiveness: Amount of time it takes to start working. (N=x)	n (%)	n (%)	n (%)	

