History of Skin Cancer		
Yes		
No		
p -value		
Prior Treatment Experience: Use of Cryosurgery		
Yes		
No		
p -value		
Prior Treatment Experience: Use of Other Topical Treatments		
Yes		
No		

p -value		
Prior Treatment Experience: Treatment Naïve at Baseline		
Yes		
No		
p -value		

P-values correspond to difference between strata within respective time periods.

Table 2.24 Subgroup Analysis of Clinician's Relative Satisfaction of Tirbanibulin, Regarding its Convenience / Ease of Use

% Much / Somewhat Better	Week 8 n (%)	Week 24 n (%)
Subgroups		
Gender		
Male		
Female		
p -value		
Age Group		
≤ 49 years		
50 – 64 Years		
≥ 65 years		
p -value		
AK Treatment Location		
Face		
Scalp		
Both		
p -value		
Fitzpatrick Skin Type		
I / II		
III / IV / V / VI		
p -value		
Skin Photodamage		
Absent/mild		
Moderate/Severe		
p -value		
History of Skin Cancer		
Yes		
No		
p -value		
Prior Treatment Experience: Use of Cryosurgery		
Yes		
No		
p -value		
Prior Treatment Experience: Use of Other Topical Treatments		
Yes		
No		

p -value		
Prior Treatment Experience: Treatment Naïve at Baseline		
Yes		
No		

P-values correspond to difference between strata within respective time periods.

Table 2.25 Subgroup Analysis of Clinician's Overall Satisfaction with Tirbanibulin Relative to Previous Topical Treatments

% Much / Somewhat Better	Week 8 n (%)	Week 24 n (%)
Subgroups		
Gender		
Male		
Female		
p -value		
Age Group		
≤ 49 years		
50 – 64 Years		
≥ 65 years		
p -value		
AK Treatment Location		
Face		
Scalp		
Both		
p -value		
Fitzpatrick Skin Type		
I / II		
III / IV / V / VI		
p -value		
Skin Photodamage		
Absent/mild		
Moderate/Severe		
p -value		
History of Skin Cancer		
Yes		
No		
p -value		
Prior Treatment Experience: Use of Cryosurgery		
Yes		
No		
p -value		
Prior Treatment Experience: Use of Other Topical Treatments		
Yes		
No		

p -value		
Prior Treatment Experience: Treatment Naïve at Baseline		
Yes		
No		

P-values correspond to difference between strata within respective time periods.

Table 2.26 Factors Influencing Overall Clinician Satisfaction with Tirbanibulin in the Original Treated Area

EPQ8 What factors influenced your response to the previous question about your overall satisfaction with tirbanibulin (Klisyri®)? **Selected**

Domain	Week 8 N=x	Week 24 N=x

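### The satisfaction-factor tables pool better, same and worse ratings, so no planned summary links a selected factor to the rating it is meant to explain

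*SAP*

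**What the plan says.** The purpose is stated twice in each document, once for subjects and once for site investigators (protocol 8.2.1, a number used for both subsections; SAP 5.2.3 and 5.2.1). The subject version begins "To complement the overall satisfaction question, factors associated with" and goes on to name the satisfaction rating.

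That rating is the comparison with other topical treatments: TT5 for patients, EPQ7 for clinicians, and RS5 for both after retreatment with another topical. It has five points, from "My satisfaction is much better with tirbanibulin" to "My satisfaction is much worse with tirbanibulin".

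The follow-up item for patients (Table 1.23) asks "What factors influenced your response to the previous question (TT5) about your overall satisfaction with tirbanibulin". The clinician item (Table 2.26) asks "What factors influenced your response to the previous question about your overall satisfaction with tirbanibulin". The options are worded without direction, for example "Product effectiveness: Impact on skin appearance"; three of them concern the time to resolution, the number and type, and the severity of local skin reactions. Respondents are then told "please identify the three most important factors and rank them on a scale of importance from 1 to 3".

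Tables 1.23 and 2.26 have a Week 8 and a Week 24 column with n (%). The ranking tables (1.24, 1.25, 2.27, 2.28) show ranks 1 to 3 and an average rank. The retreatment tables (1.32 to 1.34 and 2.42 to 2.44) follow the same pattern. SAP 6.6.1 does not mention the factor items, and SAP 6.3.1 has ad hoc questions reported individually.

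**The concern.** An association between a factor and a rating can be seen only if the two are looked at together, and these tables do not do that. A patient who rates tirbanibulin worse because the skin reactions were severe adds one to the same cell as a patient who rates it better because they were mild. The table titles speak of factors influencing satisfaction with tirbanibulin. A high count for skin-reaction severity could then be read as a tolerability advantage or as a complaint, and the table would not say which. The data needed to separate the two are held for the same respondents, so what is missing is an analysis step, at least where the comparative rating was asked.

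**Working it through.** The documents give no figure on this point, so there is nothing to reproduce. Two checks apply.

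**1. Does any planned output join the factor to the rating?**
- Factor tables: columns by week or by retreatment type, never by TT5, EPQ7 or RS5.
- Ranking tables: percentages are taken among those who chose the factor, whatever their rating.
- Tables 1.17 and 2.20 (Week 8), and 1.31 and 2.41 (after retreatment with another topical): directional ratings of duration and severity of skin reactions, daily activities, convenience and overall satisfaction, each as its own margin.
- SAP 6.3.3: the satisfaction rating is not among the subgroups.
- Protocol 12.3.4 (multivariate analyses): adjusts for baseline characteristics and variables such as adherence, where feasible. It does not name the factor items and has no counterpart section in the SAP.
- SAP Appendix D: individual listings, with no summary drawn from them.

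No planned summary joins the two.

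**2. What can be inferred from the margins alone?** Let N be the respondents, S the number selecting a factor (as in Table 1.23), B the number rating tirbanibulin better (TT5 in Table 1.17), W = N - B, and a the number who did both. The margins require only

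max(0, S - W) ≤ a ≤ min(S, B),

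and the difference in selection rate, better minus not better, is a/B - (S - a)/W.

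Take N = 100 and S = 50 (assumed). For B = 80, a lies between max(0, 50 - 20) = 30 and min(50, 80) = 50:
- a = 50: 50/80 - 0/20 = 62.5% - 0% = +62.5 points
- a = 30: 30/80 - 20/20 = 37.5% - 100% = -62.5 points

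| B (assumed) | Upper limit | Lower limit |
|---|---|---|
| 70 | 50/70 - 0/30 = +71.4 | 20/70 - 30/30 = -71.4 |
| 80 | 50/80 - 0/20 = +62.5 | 30/80 - 20/20 = -62.5 |
| 90 | 50/90 - 0/10 = +55.6 | 40/90 - 10/10 = -55.6 |
| 95 | 50/95 - 0/5 = +52.6 | 45/95 - 5/5 = -52.6 |

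In each of these cases the margins do not fix even the sign.

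A less extreme pair makes the same point. Suppose 80% rate better and 20% worse (assumed).
- Factor chosen by 25% of the first group and all of the second: 0.80 × 0.25 + 0.20 × 1.00 = 40% selected, of which 0.20/0.40 = 50% come from dissatisfied patients.
- Factor chosen by 50% of the first group and none of the second: 0.80 × 0.50 + 0.20 × 0 = 40% selected, none from dissatisfied patients.

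Both give the same cell in Table 1.23 and the same TT5 distribution in Table 1.17.

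**The case against.** The case on the other side has four parts.

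- **The purpose sentence sits in the assessment section, and SAP 6.6.1 promises no association analysis.** What the item collects is self-reported salience, and the tables report that faithfully. This is fair: the tables do show which factors respondents say they weighed and how they ranked them. But both documents speak of factors associated with the rating, and nothing planned addresses that.
- **Directional information exists elsewhere.** A reader might infer that direction cannot be recovered from any planned output. The documents do not support that. Table 1.17, for instance, shows how many patients found skin-reaction severity better or worse, and the listings may hold the linked answers. What is missing is a summary that makes the link.
- **An overall rating is not the direction of each factor.** Someone who rates tirbanibulin better overall may still hold skin reactions against it. This stands, and it limits what the split can claim.
- **The rating is not available for every factor table.** This also stands. RS5 is tabulated only for patients retreated with another topical, and no better/same/worse rating of a tirbanibulin retreatment is described. For prior-topical users, SAP 5.2.3 places the comparison at Week 8 and Table 1.17 has only Week 8, while SAP 6.6.1 and Table 1.22 also mention Week 24. Availability at Week 24 is therefore unclear.

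The comparison with previous topicals is also limited to subjects with prior topical experience, so the same and worse groups may be small.

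**Conclusion.** The point holds as a gap between what the plan says it will assess and what its tables summarise. Pooled over better, same and worse ratings, the factor counts do not show whether a factor goes with a favourable or an unfavourable rating, and the separate directional margins do not supply the link. The ranges of ±52.6 to ±71.4 points are logical limits on assumed margins. They show that the sign is not determined and do not predict the data. If nearly all respondents rate tirbanibulin better, the selections come almost entirely from satisfied respondents, although the contrast with the others stays unknown.

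A reader might go further and infer that the study's main conclusions are at risk. They are not: factor selection is a descriptive additional analysis with no p-value, and the Skindex-16 and IGA results do not depend on it. The consequence is that these tables may be misread, which a small change can prevent.

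**What to change.** - **Week 8 tables:** split Table 1.23 (Week 8 column) and Table 1.24 by TT5, and Table 2.26 (Week 8 column) and Table 2.27 by EPQ7, into better, same and worse, with n (%) per column.
- **Retreatment with another topical:** split the corresponding columns of Tables 1.32 and 2.42, and Tables 1.34 and 2.44, by RS5 in the same way.
- **Define the groups by response label as well as code.** In Tables 1.17, 2.20, 1.31 and 2.41, codes 1/2 mean better and 4/5 worse; SAP 5.2 describes the scale in the opposite order.
- **Ranking tables:** where the same or worse group is very small, collapse the groups or list the individual answers.
- **Leave unsplit:** the tirbanibulin-retreatment parts (Table 1.32 first column, Table 1.33, Table 2.42 second column, Table 2.43).
- **Week 24 (Tables 1.23, 1.25, 2.26, 2.28):** split only if the comparative rating is actually collected then, and state in the SAP whether it is.
- **SAP 6.6.1:** add a sentence that factors are reported by rating group and that this shows association with the overall rating, not the direction of each factor.

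The cost is extra columns in existing shells and one sentence of text. For the tables named in the first two items no new question or visit is needed. The drawback is sparse same and worse columns.

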7.2 Tables from Clinician's DCF (FAS Population)

Clinician data is analyzed using the FAS dataset. In relevant instances (such as IGA and physician satisfaction evaluations), only FAS dataset with corresponding week clinician data is used. All data tables in this section correspond to FAS population.

Table 2.1 Site Characteristics

Domain	(N=x)
SC1: Current workplace	
Private, office-based practice	n (%)
Hospital-based practice	n (%)
SC2: Total number of board-certified dermatologists in the practice (including yourself, if applicable)	N, Mean (SD), Median, Min, Max
SC3: At present, how many patients with AKs do you personally manage in a given month?	N, Mean (SD), Median, Min, Max
SC4: How long have you been practicing dermatology, post-residency?	N, Mean (SD), Median, Min, Max

Note: Data from Clinician DCF. The denominator for the percentage is N which refers to total number of unique sites in PROSES study.

Table 2.2 Study Subject Selection Criteria

Domain (N=X)	Yes	No
SS1r1 Diagnosed with actinic keratosis of the face and/or scalp?	n (%)	n (%)
SS1r2 Has clinically typical, visible, and discrete AK lesions?	n (%)	n (%)
SS1r3 Considered a candidate for tirbanibulin (Klisyri®) AND you plan to administer tirbanibulin (Klisyri®) treatment?	n (%)	n (%)
SS1r4 At least 18 years of age at the time of initiation of tirbanibulin (Klisyri®) treatment?	n (%)	n (%)
SS1r5 Willing to avoid excessive sun or UV exposure, and/or use relevant sunscreen protection and protective clothing during the study duration.	n (%)	n (%)
SS1r6 Able to read and write English.	n (%)	n (%)
SS1r7 Able to provide consent to participate AND is willing to comply with study procedure?	n (%)	n (%)
SS2r1 Have another dermatological condition of the face that could interfere with the actinic keratosis clinical evaluations?	n (%)	n (%)
SS2r2 Hypertrophic AK lesions, open wounds or suspected skin cancers within close proximity of the treatment area	n (%)	n (%)
SS2r3 Anticipated need for in-patient hospitalization or in-patient surgery within the next 2 months.	n (%)	n (%)
SS2r4 Have a medical chart accessible to complete baseline data collection?	n (%)	n (%)

Note: Data from Clinician DCF. The denominator for the percentage is the number of patients with available data (N=X). There are no missing data.

Table 2.3 Patient Clinical Characteristics from Medical Chart

Character	Statistics	Baseline (N=XX)
PC1 Gender		
Male	n (%)	
Female	n (%)	
Other	n (%)	
PC2 Primary Health Insurance		
Private health insurance	n (%)	
Medicaid	n (%)	
Medicare	n (%)	
Uninsured	n (%)	
Other: Self Pay	n (%)	
Not available	n (%)	
PC3 Height (in inches)	N, Mean (SD), Median, Min, Max	
PC4 Weight (in lbs/pound)	N, Mean (SD), Median, Min, Max	
PC5 Waist circumference (in inches)	N, Mean (SD), Median, Min, Max	
Body Mass Index (BMI - calculated)	N, Mean (SD), Median, Min, Max	
PC6 Blood pressure (in mm HG)		
Systolic	N, Mean (SD), Median, Min, Max	
Diastolic	N, Mean (SD), Median, Min, Max	
PC7 Concomitant (comorbid) conditions		
None	n (%)	
Anxiety	n (%)	
Anemia or other blood disease	n (%)	
Asthma	n (%)	
Atopic dermatitis	n (%)	
Cancer (of any type)	n (%)	
Crohn's disease / IBD	n (%)	
Diabetes	n (%)	
Depression	n (%)	
Dyslipidemia/Hyperlipidemia	n (%)	
Gastroesophageal reflux disease	n (%)	
Heart disease	n (%)	
Hypertension	n (%)	
Kidney disease	n (%)	

Liver damage or disease	n (%)
Lung disease	n (%)
Osteoarthritis, degenerative arthritis	n (%)
Other gastrointestinal disease	n (%)
Other	n (%)
X Y Z	n (%)

PC8 History of Skin Cancer

Yes	n (%)
No	n (%)

AK2 Fitzpatrick Skin-type classification?

Type I	n (%)
Type II	n (%)
Type III	n (%)
Type IV	n (%)
Type V	n (%)
Type VI	n (%)

Note: Data from Clinician DCF; X patients had missing data; The denominator for the percentage is the number of patients with available data (N=X)

Table 2.4 Tirbanibulin Treatment Characteristics for the Original Treated Area

Character	Baseline (N=x)
TH1B: Prescription dose 1. 1% tirbanibulin, single-dose packets 2. Other, please specify [TH1Br2oe] a. X	n (%)
TH1C: Prescription frequency 1. Once daily for 5 consecutive days 2. Other, please specify: [TH1Cr2oe] a. X	n (%)

Table 2.5 Area of Tirbanibulin Treatment for the Original Treated Area

Character	Baseline (N=x)
AK3A1: What is the AK treatment area you have identified for the patient, to apply tirbanibulin (Klisyri®)?	
Left	
Face	n (%)
Scalp	n (%)
Right	
Face	n (%)
Scalp	n (%)
Center	
Face	n (%)
Scalp	n (%)
Unknown	
Face	n (%)
Scalp	n (%)
Overall	
Face (any area)	n (%)
Scalp (any area)	n (%)

Table 2.6 Tirbanibulin Treatment Completion Rate for the Original Treated Area

Character	Week 8 (N=X)
P2: Did the patient complete 5-day treatment course of tirbanibulin (Klisyri®) at the beginning of the study? (N=X)	
Yes	n (%)
No	n (%)

Note: Data from clinician CRF.

Table 2.7 Clinician Evaluation of Current Severity of Photodamage in the Original Treated Area

Character	Baseline (N=X)	Week 8 (N=x)	Week 24 (N=X)
How do you rate the current severity of skin photodamage in the AK affected area?			
Responses will need to be recoded	AK4	AK8_3	AK8_3
0. Absent	n (%)	n (%)	n (%)
1. Mild	n (%)	n (%)	n (%)
2. Moderate	n (%)	n (%)	n (%)
3. Severe	n (%)	n (%)	n (%)
Absent/ Mild (0/1)	n (%)	n (%)	n (%)
Moderate/Severe (2/3)	n (%)	n (%)	n (%)
Who did the evaluation of patient's AK severity?			
1. Dermatologist	AK5	AK8_4	AK8_4
2. Nurse practitioner	n (%)	n (%)	n (%)
3. Physician's assistant	n (%)	n (%)	n (%)
How was the evaluation of AK severity done?			
1. During in-person patient visit (face-to-face)	AK6	AK8_5	AK8_5
2. Via tele-health visit (video)	n (%)	n (%)	n (%)

Table 2.8 CFB for Current Severity of Photodamage in the Original Treated Area

Domain	CFB in Proportion at Week 8 N=X (%)	p-value	CFB in Proportion at Week 24 N=X (%)	p-value
How do you rate the current severity of skin photodamage in the AK affected area?				
Absent (0)	%		%	
Mild / Moderate / Severe (1 / 2 / 3)	%	p	%	p
Absent / Mild (0 / 1)	%		%	
Moderate / Severe (2 / 3)	%	p	%	p

Table 2.9 Subgroup Analysis of Current Severity of Photodamage in the Original Treated Area

Subgroups	% Absent / Mild (0 / 1)		Baseline		Week 8		Week 24	
		n (%)		n (%)	P	n (%)	P	
Gender								
Male								
Female								
Age Group								
≤ 49 years								
50 – 64 Years								
≥ 65 years								
AK Treatment Location								
Face								
Scalp								
Both								
Fitzpatrick Skin Type								
I / II								
III / IV / V / VI								
Skin Photodamage								
Absent/mild								
Moderate/Severe								
History of Skin Cancer								
Yes								
No								
Prior Treatment Experience: Use of Cryosurgery								
Yes								
No								
Prior Treatment Experience: Use of Other Topical Treatments								
Yes								
No								
Prior Treatment Experience: Treatment Naïve at Baseline								
Yes								
No								

P-values correspond to CFB at respective time periods, within the corresponding strata.

Table 2.10 Clinician Evaluation of IGA in the Original Treated Area

Character	Week 8 (N=x)	Week 24 (N=X)
Overall, how is your patient's AK in the original treated area right now?		
Responses will need to be recoded	AK8_1	AK8_1
0. Completely Cleared	n (%)	n (%)
1. Partially Cleared	n (%)	n (%)
2. Moderately Cleared	n (%)	n (%)
3. Minimally Cleared	n (%)	n (%)
4. Not Cleared	n (%)	n (%)
(0 / 1) Completely/Partially Cleared	n (%)	n (%)
2 Moderately Cleared	n (%)	n (%)
3 /4 Minimally/ Not Cleared	n (%)	n (%)

Table 2.11 IGA Success at Week 8 in the Original Treated Area

Character	Week 8
IGA Success	N=x
No	n (%)
Yes	n (%)

Note: IGA success at Week 8, defined as an IGA score of completely cleared (0) or partially cleared (1) in AK status in the original treated area at Week 8. The denominator for the percentages is the number of patients with available data (N=XX). X patients had missing data at Week 8.

Table 2.12 Subgroup Analysis of IGA Success

% IGA Success (Completely/Partially Cleared)		Week 8 n (%)	Week 24 n (%)
Subgroups			
Gender			
Male			
Female			
p -value			
Age Group			
≤ 49 years			
50 – 64 Years			
≥ 65 years			
p -value			
AK Treatment Location			
Face			
Scalp			
Both			
p -value			
Fitzpatrick Skin Type			
I / II			
III / IV / V / VI			
p -value			
Skin Photodamage			
Absent/mild			
Moderate/Severe			
p -value			
History of Skin Cancer			
Yes			
No			
p -value			
Prior Treatment Experience: Use of Cryosurgery			
Yes			
No			
p -value			
Prior Treatment Experience: Use of Other Topical Treatments			
Yes			
No			
p -value			

Prior Treatment Experience: Treatment Naïve at Baseline

Yes

No

p-value

P-values correspond to difference between strata within respective time periods.

Table 2.13 Clinician Evaluation of Overall Appearance in the Original Treated Area

Character	Week 8 (N=x)	Week 24 (N=X)
Compared to 8 / 24 weeks ago, how has the patient's overall appearance of the skin in the original AK treated area changed?		
1. Much Worse	AK8_2	AK8_2
2. Somewhat Worse	n (%)	n (%)
3. No Change	n (%)	n (%)
4. Somewhat improved	n (%)	n (%)
5. Much Improved	n (%)	n (%)
(1/2) Much/Somewhat Worse	n (%)	n (%)
(3) No Change	n (%)	n (%)
(4/5) Somewhat/Much Improved	n (%)	n (%)

Table 2.14 Subgroup Analysis of Clinician Evaluation of Overall Appearance in the Original Treated Area

% Somewhat / Much Improved	Week 8 n (%)	Week 24 n (%)
Subgroups		
Gender		
Male		
Female		
p -value		
Age Group		
≤ 49 years		
50 – 64 Years		
≥ 65 years		
p -value		
AK Treatment Location		
Face		
Scalp		
Both		
p -value		
Fitzpatrick Skin Type		
I / II		
III / IV / V / VI		
p -value		
Skin Photodamage		
Absent/mild		
Moderate/Severe		
p -value		
History of Skin Cancer		
Yes		
No		
p -value		
Prior Treatment Experience: Use of Cryosurgery		
Yes		
No		
p -value		
Prior Treatment Experience: Use of Other Topical Treatments		
Yes		
No		

p -value		
Prior Treatment Experience: Treatment Naïve at Baseline		
Yes		
No		

P-values correspond to difference between strata within respective time periods.

Table 2.15 Treatment Satisfaction Questionnaire for Medication: Clinician Scores in the Original Treated Area

Domain	Week 8 N=xx	Week 24 N=xx
Effectiveness		
	Mean (SD)	Mean (SD)
	Median	Median
	Min, Max	Min, Max
Convenience		
	Mean (SD)	Mean (SD)
	Median	Median
	Min, Max	Min, Max
Global Satisfaction		
	Mean (SD)	Mean (SD)
	Median	Median
	Min, Max	Min, Max

Note: Data from Clinician DCF. Questions and scoring were based on TSQM-9

Instructions for TSQM Scoring:

Variables TS1 - TS9

TSQM			
Scoring Steps	Global Satisfaction Score	Effectiveness Score	Convenience Score
1	Sum TS7 TS8 TS9	Sum TS1 TS2 TS3	Sum TS4 TS5 TS6
2	Subtract 3	Subtract 3	Subtract 3
3	Divide 14	Divide 18	Divide 18
4	Multiple 100	Multiple 100	Multiple 100
	Output: Average Score per patient		

Table 2.16 Subgroup Analysis of Clinician Treatment Satisfaction Questionnaire for Medication Domain Scores in the Original Treated Area

Subgroups	Effectiveness			Convenience			Global Satisfaction		
	Baseline n, Mean	Wk-8 n, Mean	P	Baseline n, Mean	Wk-8 n, Mean	P	Baseline n, Mean	Wk-8 n, Mean	P
Gender									
Male									
Female									
Age Group									
≤ 49 years									
50 – 64 Years									
≥ 65 years									
AK Treatment Location									
Face									
Scalp									
Both									
BL Fitzpatrick Skin Type									
I / II									
III / IV / V / VI									
BL Skin Photodamage									
Absent/mild									
Moderate/Severe									
BL History of Skin Cancer									
Yes									
No									
Prior Treatment Experience: Use of Cryosurgery									
Yes									
No									
Prior Treatment Experience: Use of Other Topical Treatments									
Yes									
No									
Prior Treatment Experience: Treatment Naïve at Baseline									
Yes									
No									

*If sample size permits. P-values correspond to CFB at week-8, within respective strata.

Table 2.17 Clinician Satisfaction with Tirbanibulin in the Original Treated Area (looks/texture)

Domain	Week 8 (N=x)	Week 24 (N=x)
EPQ1: How satisfied are you with this treatment's ability to improve how your patient's skin looks (example: reduced redness, discoloration, crusting, scaling), in the original AK treated area?	Mean (SD), Median, Min,Max	Mean (SD), Median, Min,Max
1. Extremely Dissatisfied	n (%)	n (%)
2. Very Dissatisfied	n (%)	n (%)
3. Dissatisfied	n (%)	n (%)
4. Somewhat Satisfied	n (%)	n (%)
5. Satisfied	n (%)	n (%)
6. Very Satisfied	n (%)	n (%)
7. Extremely Satisfied	n (%)	n (%)
8. Don't know / not applicable	n (%)	n (%)
(1 / 2) Extremely/Very Dissatisfied		
(3 / 4 / 5) Dissatisfied/Somewhat Satisfied/Satisfied	n (%)	n (%)
(6 / 7) Very/Extremely Satisfied	n (%)	n (%)
EPQ2: How satisfied are you with this treatment's ability to improve your patient's skin texture (i.e., how the skin feels in terms of roughness, bumpiness, scaliness) as a result of the treatment, in the original AK treated area?	Mean (SD), Median, Min,Max	Mean (SD), Median, Min,Max
1. Extremely Dissatisfied	n (%)	n (%)
2. Very Dissatisfied	n (%)	n (%)
3. Dissatisfied	n (%)	n (%)
4. Somewhat Satisfied	n (%)	n (%)
5. Satisfied	n (%)	n (%)
6. Very Satisfied	n (%)	n (%)
7. Extremely Satisfied	n (%)	n (%)
8. Don't know / not applicable	n (%)	n (%)
(1 / 2) Extremely/Very Dissatisfied	n (%)	n (%)
(3 / 4 / 5) Dissatisfied/Somewhat Satisfied/Satisfied	n (%)	n (%)
(6 / 7) Very/Extremely Satisfied	n (%)	n (%)

Table 2.18 Subgroup Analysis of Clinician Satisfaction with Treatment Ability to Improve How Skin Looks in the Original Treated Area

% Extremely/Very Satisfied		Week 8 n (%)	Week 24 n (%)
Subgroups			
Gender			
Male			
Female			
p -value			
Age Group			
≤ 49 years			
50 – 64 Years			
≥ 65 years			
p -value			
AK Treatment Location			
Face			
Scalp			
Both			
p -value			
Fitzpatrick Skin Type			
I / II			
III / IV / V / VI			
p -value			
Skin Photodamage			
Absent/mild			
Moderate/Severe			
p -value			
History of Skin Cancer			
Yes			
No			
p -value			
Prior Treatment Experience: Use of Cryosurgery			
Yes			
No			
p -value			
Prior Treatment Experience: Use of Other Topical Treatments			

Yes		
No		
p -value		
Prior Treatment Experience: Treatment Naïve at Baseline		
Yes		
No		
p -value		

P-values correspond to difference between strata within respective time periods.

Table 2.19 Subgroup Analysis of Patient Satisfaction with Treatment Ability to Improve Skin Texture in the Original Treated Area

% Extremely/Very Satisfied	Week 8 n (%)	Week 24 n (%)
Subgroups		
Gender		
Male		
Female		
p -value		
Age Group		
≤ 49 years		
50 – 64 Years		
≥ 65 years		
p -value		
AK Treatment Location		
Face		
Scalp		
Both		
p -value		
Fitzpatrick Skin Type		
I / II		
III / IV / V / VI		
p -value		
Skin Photodamage		
Absent/mild		
Moderate/Severe		
p -value		
History of Skin Cancer		
Yes		
No		
p -value		
Prior Treatment Experience: Use of Cryosurgery		
Yes		
No		
p -value		
Prior Treatment Experience: Use of Other Topical Treatments		
Yes		
No		

p -value		
Prior Treatment Experience: Treatment Naïve at Baseline		
Yes		
No		
p -value		

P-values correspond to difference between strata within respective time periods.

Table 2.20 Clinician Relative Satisfaction of Tirbanibulin in Comparison with Other Topical Medications for AK in the Original Treated Area

Domain	Week 8 (N=x)	
EPQ3: Compared to your patient's previous experience with topical treatment X for AK, how would you rate the duration of skin reactions (i.e., how long the skin reactions lasted) associated with tirbanibulin (Klisyri®) that the patient experienced in the original AK treated area?		Mean (SD), Median,Min,Max
1. Duration of skin reactions was much shorter with tirbanibulin	n (%)	
2. Duration of skin reactions was somewhat shorter with tirbanibulin	n (%)	
3. Duration of skin reactions was the same with tirbanibulin	n (%)	
4. Duration of skin reactions was somewhat longer with tirbanibulin	n (%)	
5. Duration of skin reactions was much longer with tirbanibulin	n (%)	
(1 / 2) Duration of skin reactions was much / somewhat shorter with tirbanibulin	n (%)	
(3) Duration of skin reactions was the same with tirbanibulin	n (%)	
(4 / 5) Duration of skin reactions was somewhat / much longer with tirbanibulin	n (%)	
EPQ4: Compared to your patient's previous experience with topical treatment X for AK, how would you rate the severity of skin reactions (i.e., how bad the skin reactions were) associated with tirbanibulin (Klisyri®) that the patient experienced in the original AK treated area?		Mean (SD), Median,Min,Max
1. Severity of skin reactions was much better with tirbanibulin	n (%)	
2. Severity of skin reactions was somewhat better with tirbanibulin	n (%)	
3. Severity of skin reactions was the same with tirbanibulin	n (%)	
4. Severity of skin reactions was somewhat worse with tirbanibulin	n (%)	
5. Severity of skin reactions was much worse with tirbanibulin	n (%)	
(1 / 2) Severity of skin reactions was much / somewhat better with tirbanibulin	n (%)	
(3) Severity of skin reactions was the same with tirbanibulin	n (%)	
(4 / 5) Severity of skin reactions was much / somewhat worse with tirbanibulin	n (%)	
